The Use of Clear Aligners with Movement Enhancement Techniques NCT02087163

January 9, 2019

Study Summary

Title	The Use of Clear Aligners with Movement Enhancement Techniques
Objectives	Evaluated whether movement enhancement techniques increased the rate and length of tooth movement, and length of total treatment time.
Purpose	The purpose of this study was to use clear aligners to measure tooth
	movement and length of treatment.
Relevant Scientific	Orthodontic tooth movement is the result of forces applied to the crown of a
Background	tooth and the biological remodeling of the soft and hard tissues.
	The Invisalign® System (Align Technology, San Jose, California, USA)
	accurately fabricates removable clear aligners to move teeth with relative
	precision to provide comprehensive orthodontic treatment. Some
	practitioners advise patients to change aligners at 1-2 week wear time
	intervals in order to reduce treatment time or for other orthodontic or dental
	reasons. Animal studies in mice and rats have suggested that low magnitude,
	high frequency mechanical stimuli increases the healing of bony lesions in
	non-weight bearing bones, enhances the adaptive remodeling of condylar
	cartilage as evidenced by the advent of endochondral bone replacing
	hypertrophic cartilage, and enhances the effect of mechanical and magnetic
	forces on tooth movement.
Design	This was a non-significant risk, multicenter, randomized prospective study
	conducted at three sites in North America. A total of 90 adult patients who
	were eligible for Invisalign® Full treatment per the standard Invisalign®
	Instructions for Use were recruited for the study. Subjects were randomly
	placed into either a 7 day or 14 day aligner wear schedule.
Primary Outcome	Tooth movement change was calculated.
	 Participants were followed for the duration of orthodontic treatment, an average of 78 weeks.
Secondary Outcome	Length of treatment change was calculated as number of clear aligners used.
	Participants were followed for the duration of orthodontic treatment, Participants were followed for the duration of orthodontic treatment, Participants were followed for the duration of orthodontic treatment, Participants were followed for the duration of orthodontic treatment, Participants were followed for the duration of orthodontic treatment, Participants were followed for the duration of orthodontic treatment, Participants were followed for the duration of orthodontic treatment, Participants were followed for the duration of orthodontic treatment, Participants were followed for the duration of orthodontic treatment, Participants were followed for the duration of orthodontic treatment, Participants were followed for the duration of orthodontic treatment, Participants were followed for the duration of orthodontic treatment, Participants were followed for the duration of orthodontic treatment, Participants were followed for the duration of orthodontic treatment, Participants were followed for the duration of orthodontic treatment, Participants were followed for the duration of orthodontic treatment, Participants were followed for the duration of orthodontic treatment, Participants were followed for the duration of orthodontic treatment, Participants were followed for the duration of orthodontic treatment, Participants were followed for the duration of orthodontic treatment, Participants were followed for the duration of orthodontic treatment, Participants were followed for the duration of orthodontic treatment, Participants were followed for the duration of orthodontic treatment, Participants were followed for the duration of orthodontic treatment, Participants were followed for the duration of orthodontic treatment, Participants were followed for the duration of orthodontic treatment, Participants were followed for the duration of orthodontic treatment, Participants wer
	an average of 78 weeks.
Treatment	Clear aligners with movement enhancement techniques.
· · · · · · · · · · · · · · · · · · ·	

Eligibility Criteria	Inclusion Criteria:
	A subject were considered eligible if all of following inclusion criteria were fulfilled:
	Males or females between the ages of 16-46 inclusive
	Required orthodontic treatment
	Had permanent dentition
	No craniofacial anomaly present
	No past and present signs and symptoms of periodontal disease
	 No significant medical history or medication that would adversely affect the development or structure of the teeth and jaws and any subsequent tooth movement
	No previous orthodontic or orthopaedic relapse
	No history of trauma, bruxism or parafunction
	No skeletal jaw discrepancy
	Angle Class I or Class II molar and canine relationship
	Crowding of at least 4mm per arch
	No osteoporosis drugs
	Exclusion Criteria:
	A subject was considered ineligible if any one of the following exclusion criteria were fulfilled:
	Subjects who did not fulfill all inclusion criteria requirements
Sites	3 participating doctors in the North America.
Sample Size	90 subjects.
Length of Study	Approximately 4 years.
Statistical Analysis	Pretreatment records were analyzed to measure the exact amount of
Plan	crowding. A discriminate analysis was used to ensure that there was no
	significant difference between study groups in any parameters (crowding, overjet, overbite, crossbite, gender, age, race,) that may have impacted the
	analysis of the efficacy of the aligners and the aligners with movement enhancement techniques.
	A multivariate analysis was conducted to determine if time or treatment modality showed an effect.

	Rate of tooth movement, length of treatment, and length of total treatment time were analyzed between all study groups.
	A sample size of 90 was selected to determine if future studies should be conducted based on the outcome of this study.
Results	Subject Enrollment
	 Started: 90 70 female 20 male Completed: 73 Not completed: 17 All 73 completed subjects were included in the data analysis which was conducted by Align's own statisticians. Tooth movement change was
	measured as a millimeters of change per aligner. Length of treatment change was measured as the number of weeks. No Adverse Events were reported.

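### The sole listed secondary outcome is defined as an aligner count but reported in weeks, and a count cannot compare treatment time between 7-day and 14-day wear

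*Combined protocol and SAP*

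**What the plan says.** All the relevant text is in the Study Summary table of the combined protocol and SAP.

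- **Secondary Outcome row:** "Length of treatment change was calculated as number of clear aligners used". No other secondary outcome is listed.
- **Results row:** "Length of treatment change was measured as the number of weeks". The label is identical and the unit is different.
- **Design row:** subjects were randomly "placed into either a 7 day or 14 day aligner wear schedule". This is the only randomised contrast described.
- **Primary Outcome row (follow-up):** "Participants were followed for the duration of orthodontic treatment, an average of 78 weeks". The average is not split by arm.
- **Statistical Analysis Plan row:** length of treatment and length of total treatment time are named as two separate analysed quantities. Neither is given a unit.
- **Objectives row:** "Evaluated whether movement enhancement techniques increased the rate and length of tooth movement, and length of total treatment time". Time is tied here to movement enhancement, not to the wear schedule.
- **Relevant Scientific Background row:** one reason given for changing aligners every one to two weeks is to shorten treatment ("intervals in order to reduce treatment time").

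**The concern.** One outcome label carries two units, and both statements are current text. In a trial where everyone changed aligners at the same interval this would be a matter of wording, because count and weeks would be proportional. Here the interval is what was randomised. The count then mixes two things: how many steps the treatment took, and how long each step was set to last. It cannot serve as a measure of time across the arms.

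At stake is the direction of the answer. Someone who followed the written definition and compared aligner counts between the schedules could conclude that 7-day wear lengthened treatment when it shortened it. Someone who used the unit in the Results row would conclude the opposite from the same subjects. The document does not say which unit was prespecified or why they differ.

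**Working it through.** The document gives no derived figure for this outcome, so there is none to reproduce. The check is unit arithmetic.

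**Inputs**

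- Wear interval: 7 or 14 days per aligner (Design row).
- 78 weeks: average follow-up over all subjects (Primary Outcome row), used only to set a realistic scale.
- Assumption: each aligner is worn for its assigned interval.

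**Conversion.** Weeks = aligners × interval in days / 7. Write N7 and N14 for the aligner counts in the two arms.

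- 7-day arm: weeks = N7 × 7/7 = N7
- 14-day arm: weeks = N14 × 14/7 = 2 × N14

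**Ratio.** Weeks ratio (7-day/14-day) = N7 / (2 × N14) = 0.5 × (N7/N14). The factor is constant within an arm, so the same relation holds for arm means.

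**Reversal.** More aligners on 7-day wear requires N7 > N14. Fewer weeks requires N7 < 2 × N14. Both hold when N14 < N7 < 2 × N14, that is, for a count ratio strictly between 1 and 2.

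**On the 78-week scale.** 78 weeks = 546 days, which is 546/7 = 78 aligners on 7-day wear and 546/14 = 39 on 14-day wear. Take 39 aligners on 14-day wear (78 weeks) as the comparator:

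| Aligners, 7-day | Weeks, 7-day | Count ratio | Weeks ratio | Reading |
|---|---|---|---|---|
| 39 | 39 | 1 | 0.5 | same count, half the time |
| 40 to 77 | 40 to 77 | between 1 and 2 | between 0.5 and 1 | more aligners, less time |
| 78 | 78 | 2 | 1 | twice the count, same time |

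**Time without aligner wear.** Add the same G weeks to both arms. The condition N7 + G < 2 × N14 + G reduces to N7 < 2 × N14, so the reversal range is unchanged. At equal counts N the weeks ratio becomes (N + G)/(2N + G), which is 0.5 when G = 0 and stays below 1 for any G.

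**Within one schedule.** The conversion factor is the same for every subject, so count and weeks rank subjects identically and no reversal can occur.

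**The case against.** The strongest reply is that weeks, the right unit for time, is what the Results row reports, so the count definition did no harm. On its face weeks was the unit used, and that limits the consequence. It does not explain the departure from the written definition. Nor does it tell the reader whether weeks were recorded or obtained by multiplying the count by the assigned interval. Derived weeks would miss any departure from the schedule.

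A second reply is that two measures were intended, with aligners for length of treatment and weeks for length of total treatment time. The Statistical Analysis Plan row does name both. However, the Results row attaches weeks to the very label that the Secondary Outcome row defines by aligners, so the text cannot confirm that reading. If it is correct, saying so settles the matter.

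A third is that the stated objective concerns movement enhancement, not wear schedule. This also stands as a limit. The document does not say how enhancement relates to the two schedules. If enhancement groups were compared within one schedule, the units would be proportional and the problem would not arise for that objective.

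Finally, the reversal is illustrative. There are no counts, weeks, tests or conclusions by arm, and nothing shows that the observed count ratio fell between 1 and 2.

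**Conclusion.** The concern holds. The sole listed secondary outcome has two incompatible units in current text, and the one in its definition cannot measure treatment time across the only randomised contrast described. At the assigned intervals the two measures differ by a factor of 2 in the arm ratio, and they point in opposite directions for any count ratio strictly between 1 and 2. This rests on subjects keeping to their assigned interval and on time without aligner wear, if any, being equal in the two arms.

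Confidence is high for the conflict and the arithmetic. An effect on the trial's actual conclusion is possible but not demonstrated, and whether the enhancement objective is touched cannot be determined. This should be fixed, but it is a matter of definition and reporting and does not by itself invalidate the trial.

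**What to change.** 1. Reconcile the Secondary Outcome and Results rows, and state why the reported unit differs from the defined one.
2. Report aligners used and treatment duration in weeks as two separately labelled outcomes, each by arm. Say which corresponds to length of treatment and which to length of total treatment time in the Statistical Analysis Plan row.
3. Base any 7-day versus 14-day statement about treatment time on weeks.
4. Say whether weeks were recorded or derived from the count and the assigned interval.

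The cost is relabelling, one or two clarifying sentences and a small table. If weeks were not recorded, a short re-derivation is needed. The sponsor should confirm that both quantities exist for the 73 analysed subjects (90 started − 17 not completed). The design does not change. How the enhancement groups relate to the wear schedules is a separate gap; stating it would let a reader see whether the unit conflict reaches the stated objective.

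### The secondary outcome is called a change but is a raw total with no reference value, and measured crowding is stated only for a balance check, not for adjustment

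*Combined protocol and SAP*

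**What the plan says.** All references are to the Study Summary table of the combined protocol and SAP.

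- **Secondary Outcome row:** "Length of treatment change was calculated as number of clear aligners used".
- **Results row:** "Length of treatment change was measured as the number of weeks". Neither row names a baseline, a planned value or any other reference.
- **Design row:** subjects were randomly "placed into either a 7 day or 14 day aligner wear schedule". The allocation ratio is not given.
- **Statistical Analysis Plan row:** "Pretreatment records were analyzed to measure the exact amount of" crowding. Crowding, overjet, overbite, crossbite, gender, age and race are described as parameters that could have affected the efficacy analysis. They enter a discriminant analysis meant to show no significant group difference. A multivariate analysis follows that names only time and treatment modality. No covariates are listed.
- **Results row, analysis set:** "All 73 completed subjects were included in the data analysis", out of 90 who started.

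**The concern.** A total observed once per subject is not a change from anything. It contains whatever the schedule did and also how much movement the case needed. If nothing in the model accounts for case size, that variation stays in the error term, and any chance difference in case size between the arms passes into the estimate in proportion to its correlation with the outcome.

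The plan recognises that crowding could matter and has measured it. The stated response, though, is a significance check of balance. A non-significant result does not show that the arms are alike when there are 73 subjects, and it does nothing for precision even when they are alike. At stake is the width of the interval for the secondary comparison, in a study whose stated aim is to decide whether further studies are worthwhile.

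**Working it through.** **The plan's own figure.** The sample size of 90 cannot be reproduced, because no alpha, power, effect size or SD is given. The stated reason is: "A sample size of 90 was selected to determine if future studies should be conducted based on the outcome of this study". The counts do agree: 70 + 20 = 90 and 73 + 17 = 90, with 17/90 = 18.9% not completing.

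**Inputs**
- From the documents: 73 analysed; two schedules; crowding measured before treatment.
- Assumed: a 37/36 split, two-sided 5%, and 80% power where detectable differences are given.
- Assumed: a within-arm correlation r between covariate and outcome of 0.3, 0.5 or 0.7.

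**Step 1: unadjusted precision, in SDs of the outcome**
- SE = √(1/37 + 1/36) = 0.234.
- 95% half-width = t(0.975, 71 df) × SE = 1.994 × 0.234 = 0.467.
- Detectable difference = (1.960 + 0.842) × 0.234 = 0.656.

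**Step 2: what the balance check can miss.** The SE of a chance difference in mean crowding is also 0.234, in SDs of crowding. A single-variable 5% test therefore does not reject until the difference reaches about 0.467 SD. The outcome estimate shifts by r × the imbalance:

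| r | one-SE imbalance (0.234 SD) | imbalance just short of significance (0.467 SD) |
|---|---|---|
| 0.3 | 0.07 SD | 0.14 SD |
| 0.5 | 0.12 SD | 0.23 SD |
| 0.7 | 0.16 SD | 0.33 SD |

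The discriminant analysis uses several parameters together and its test level is not given, so 0.467 SD is a guide to its sensitivity, not its actual threshold.

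**Step 3: covariate adjustment.** Residual variance is multiplied by 1 − r², ignoring the one degree of freedom spent. The half-width is 0.467 × √(1 − r²):

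| r | variance cut | half-width | detectable difference |
|---|---|---|---|
| 0 (raw) | 0% | 0.467 SD | 0.656 SD |
| 0.3 | 9% | 0.45 SD | 0.626 SD |
| 0.5 | 25% | 0.40 SD | 0.568 SD |
| 0.7 | 49% | 0.33 SD | 0.468 SD |

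**Step 4: a literal change score.** Suppose a planned aligner count existed and a simple difference, used minus planned, were analysed. With equal SDs its variance factor is 2(1 − r), which is 1.4, 1.0 and 0.6 at r = 0.3, 0.5 and 0.7. The detectable differences are 0.776, 0.656 and 0.508 SD. That is worse than the raw total at 0.3, no better at 0.5, and behind covariate adjustment at all three values.

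**Step 5: the unit.** The follow-up of "an average of 78 weeks" corresponds to 78/1 = 78 aligners at 7 days each or 78/2 = 39 at 14 days. If wear follows the schedule, log weeks equals log aligners plus a constant for the arm (0 or log 2). The covariate then gives the same precision on the log scale in either unit. The schedule effect itself moves by log 2 = 0.693, so the unit must be settled before the result can be read.

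**The case against.** Several arguments on the other side have force.

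- **It is a labelling matter.** The Statistical Analysis Plan row speaks of length of treatment, without the word change, compared between groups. A plain reading is a between-arm comparison of totals. This stands as far as the word goes, and deleting it answers that part. It does not answer the missing adjustment.
- **The plan does attend to case size.** It measures crowding and checks balance, and the multivariate analysis may have included covariates that are not listed. The check would flag a gross imbalance. It still removes no variance, and unlisted covariates cannot be credited.
- **Randomisation protects the comparison.** This is correct. A reader might infer that the raw total biases the arm comparison. Across all randomised subjects, case size adds noise and chance imbalance, not systematic bias. Analysing only 73 of 90 weakens the assurance of balance, but that is a separate question.
- **The gain is unproven.** This is also correct. The documents give neither r nor an SD.

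A reader might also infer that case size dominates the total and varies widely, because entry requires "Crowding of at least 4mm per arch" with no upper limit. A missing ceiling is not evidence of wide spread. Other criteria narrow the mix: Angle Class I or II only, and no skeletal discrepancy.

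**Conclusion.** The point holds in a modest form. The outcome has no reference value, its unit differs between two rows, and a measured baseline variable that the plan itself regards as relevant has no stated role in the comparison. Using that variable as a covariate is better than testing it for balance.

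The size is conditional on r. Under the assumed 37/36 split, the half-width of 0.47 SD falls to between 0.45 SD (r = 0.3) and 0.33 SD (r = 0.7). If crowding is nearly unrelated to length of treatment, the gain is close to nil.

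A stronger conclusion is tempting: that each subject's initially planned aligner count is the natural starting value and would recover large amounts of precision. The documents do not support it. They mention no planned count, and so do not show that one was recorded or fixed before allocation. If it was set with the schedule known, adjusting for it could remove part of the effect.

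**What to change.** 1. State one unit for the secondary outcome and use it in both the Secondary Outcome and Results rows. Drop the word change, or name the reference from which it is taken.
2. Compare arms by regressing log length of treatment on schedule, with pretreatment crowding as a covariate. State how the two arches are combined, and list any other covariates in the multivariate analysis.
3. Add log planned aligner count as a further covariate only if it was recorded and fixed before allocation. Do not make a simple used-minus-planned difference the main analysis.
4. Report baseline crowding by arm descriptively, in place of relying on a significance check.

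The cost is revised wording and one more regression on data the trial should already hold, since crowding was measured. No new patient data are needed for crowding. Whether a planned count can be retrieved is unknown. Because results have already been produced, the adjusted analysis must be labelled post hoc and shown beside the unadjusted one.

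### A non-significant baseline test cannot ensure balance, and the plan names no baseline covariate or site term: at an assumed two-sided 0.05 level, a crowding difference of up to 0.42–0.47 SD passes

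*Combined protocol and SAP*

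**What the plan says.** All of this is in the Study Summary table of the combined protocol and SAP.

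- **Baseline check (Statistical Analysis Plan row).** "A discriminate analysis was used to ensure that there was no" "significant difference between study groups in any parameters". Seven are listed: crowding, overjet, overbite, crossbite, gender, age and race. They are described as variables that may have affected the "analysis of the efficacy of the aligners and the aligners with movement enhancement techniques".
- **Crowding.** It is singled out for measurement: "Pretreatment records were analyzed to measure the exact amount of" crowding. Eligibility is set per arch: "Crowding of at least 4mm per arch".
- **Outcome analysis.** "A multivariate analysis was conducted to determine if time or treatment modality showed an effect". The next sentence adds: "Rate of tooth movement, length of treatment, and length of total treatment time were analyzed between all study groups". No baseline covariate and no site term is named.
- **Design and Results rows.** Three sites, random allocation to a 7-day or 14-day wear schedule, 90 started, and 73 completed and analysed.

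The plan gives no significance level, form of test, allocation ratio or per-arm numbers. It does not say whether the baseline check used the 90 or the 73, or what would follow from a significant result.

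**The concern.** Failing to reject a null hypothesis of no difference is not evidence of balance. With a few dozen subjects per arm, a visible difference in crowding can fall short of significance. The plan itself treats these variables as able to influence the efficacy comparison, yet it relies on the test to dispose of them and describes no adjustment.

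Two things are at stake. The first is precision: variance that crowding and site could explain is left in the error term. The second is the reading of this one trial: if crowding is related to the outcome and the arms happen to differ on it, the unadjusted comparison is shifted, while the reader has been told that balance was secured. The sample-size statement says the result is meant to inform whether further studies are run.

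**Working it through.** The plan states no figure on this point, so there is none to reproduce.

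**Inputs.** From the documents: N=90 started, N=73 analysed, two schedules, seven baseline variables, three sites. Assumed: arms of about equal size (45/45 or 37/36), a 0.05 level (two-sided for the single-variable test), one term per variable, one outcome value per subject. The crowding–outcome correlation r is not given; 0, 0.3 and 0.5 are used.

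**1. Largest crowding difference that passes a single-variable test.** d = t(0.975, N−2) × √(1/n1 + 1/n2).
- N=90: 1.987 × 0.2108 = 0.419 SD.
- N=73: 1.994 × 0.2341 = 0.467 SD.
- At a 0.10 level the range is 0.35–0.39 SD; at 0.01 it is 0.56–0.62 SD. Unequal arms raise it: 0.44–0.50 SD at about 1:2.

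**2. Joint seven-variable test.** A two-group discriminant analysis is equivalent to Hotelling's T². The critical value is T² = 7(N−2)/(N−8) × F(0.95; 7, N−8), and the limit for crowding is √(T² × (1/n1 + 1/n2)).
- N=90: F = 2.123, T² = 15.95, limit 0.842 SD.
- N=73: F = 2.154, T² = 16.47, limit 0.950 SD.

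This is an algebraic limit, reached only if all the distance between groups lies on crowding. Under randomisation, a chance crowding difference that large has probability of about 0.00013 at either N.

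**3. Type I error averaged over trials that pass (simulation, 37/36).** For r = 0, 0.3, 0.5, the unadjusted t-test gives 5.0%, 4.8%, 4.3% after a single-variable check and about 5.0%, 5.0%, 4.8% after a joint check.

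**4. Type I error at a fixed imbalance (37/36).** Given imbalance d, the group difference is centred on r×d outcome SDs with standard error 0.2341 × √(1−r²), while the test still rejects beyond about 0.467. At d = 0.4:
- r = 0.3: centre 0.12, standard error 0.2233. The tails are at (0.467−0.12)/0.2233 = 1.55 and (0.467+0.12)/0.2233 = 2.63, giving about 6.5%.
- r = 0.5: centre 0.20, standard error 0.2027. The tails are at 1.32 and 3.29, giving about 9.5%.

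Simulation, which allows for the estimated SD, gives 5.0%, 6.9% and 10.0% for r = 0, 0.3 and 0.5. At d = 0.467 it gives 5.0%, 8.0% and 13.1%. At d = 0.24, about one standard error, it stays near 5%. A model with schedule, crowding and site holds about 5% at both larger imbalances.

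**5. How often that happens.** At 37/36, P(|d| > 0.4) = 0.092. Removing the 0.050 that fail a single-variable check leaves 0.042, about 4% of trials. With a joint check it is about 8% (0.077 by simulation). At 45/45 the single-variable figure is smaller: 0.4/0.2108 = 1.90 on 88 df gives 0.061, and 0.061 − 0.050 = 0.011.

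**6. Precision (N=73).** Variance ratio, adjusted to unadjusted = (1−R²) × (N−3)/(N−3−k), with k = 3 (total crowding plus two site terms) or k = 4 (one crowding term per arch plus two site terms).

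| R² | k=3 | k=4 |
|---|---|---|
| 0 | 1.045 | 1.061 |
| 0.1 | 0.940 | 0.955 |
| 0.2 | 0.836 | 0.848 |
| 0.3 | 0.731 | 0.742 |

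Break-even R² = k/70: 0.043 or 0.057. If R² = 0, the standard error grows by √1.045 = 1.022 or √1.061 = 1.030.

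**The case against.** The strongest reply is that randomisation already does the work. Step 3 bears this out: across trials that pass the check, the unadjusted test keeps its error at or below about 5%. The inflated rates need an imbalance that nobody has reported and a correlation that the documents do not give; at r = 0 nothing happens. All of that stands, and it limits the point to precision and to conditional protection. The precision gain also rests on an unknown R²; below about 4–6%, adjustment costs a little.

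The joint-test limit of 0.84–0.95 SD could be read as a realistic hazard. It is not: such a chance imbalance is a roughly 1-in-8,000 event. The wording about any of the parameters also suggests variable-by-variable checking, for which 0.42–0.47 SD is the relevant bound.

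The text is a few sentences in the past tense and states the question asked of the multivariate analysis, not a full model. A reader might infer that no adjustment was made; the documents show only that none is specified.

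It is also fair to ask why one listed variable and site should be chosen once results exist. The reasons are that crowding is the variable the plan measured exactly, site is part of the design, and 73 subjects support few terms. The choice is still post hoc and must be labelled so. Finally, the adjusted model's 5% in step 4 comes from a simulation in which that model is correct by construction.

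**Conclusion.** The concern holds in a limited form. The baseline test does not support the assurance placed on it, and adjusting for crowding and site is a better, cheap way to deal with variables that the plan itself considers influential. The sizes rest on two near-equal arms and a 0.05 level. If treatment modality defines further groups, the numbers per group fall and the passing differences rise.

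A reader might go further and conclude that the arms were unbalanced or that the reported comparison is biased. The documents support neither: they give no group-level baseline data, no crowding–outcome correlation and no R². Harm in this trial is possible, not shown. This is a recommended improvement to analysis and reporting, not a defect that invalidates the result.

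Three neighbouring matters are separate and add no weight here: length of treatment counted in aligners in one row and in weeks in another, the unclear modality groups, and the 17 who did not complete.

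**What to change.** 1. Remove the claim that the discriminant analysis ensures balance, and do not use a baseline test for that purpose.
2. Report the seven baseline variables by randomised group, without p-values, for the 90 randomised and for the 73 analysed.
3. Whatever any baseline test showed, fit a model labelled post hoc with randomised schedule, the plan's other effects of interest, continuous baseline crowding (total, or one term per arch, since eligibility is per arch) and site (three levels). Where measures are repeated over time, allow for within-subject correlation. Present it beside the unadjusted result.
4. State which terms the original multivariate analysis contained.
5. Pre-specify the same covariates in any follow-on study.

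The cost is one further model per outcome on data that the plan says were collected, one baseline table, and 3–4 degrees of freedom, with the standard-error penalty in step 6 if the covariates explain nothing. Adjustment does not by itself remove any bias from analysing completers only, and the length-of-treatment measure has to be reconciled before a model for it can be interpreted.

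### The only analysis set named is the 73 completers of 90 starters, so the 7-day v 14-day comparison is not the randomised one and is open to selection bias of unknown presence, direction and size

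*Combined protocol and SAP*

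**What the plan says.** The Design row of the Study Summary describes a randomised multicentre study in which subjects were randomly "placed into either a 7 day or 14 day aligner wear schedule". It gives no allocation ratio or arm sizes.

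The Results row gives 90 started, 73 completed and "Not completed: 17", followed by "All 73 completed subjects were included in the data analysis". It does not say in so many words that the 17 were excluded. It does not define completion, and it does not say that starting means being randomised. Tooth movement was "measured as a millimeters of change per aligner"; for the other outcome the row says "Length of treatment change was measured as the number of weeks".

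The Statistical Analysis Plan row says: "Rate of tooth movement, length of treatment, and length of total treatment time were analyzed between all study groups". It names no analysis set, no rule for subjects who stop early, no missing-data method and no sensitivity analysis. It does describe a discriminant analysis between study groups on crowding, overjet, overbite, crossbite, gender, age and race, without saying whether this used 90 or 73 subjects. It gives the purpose of the 90 as deciding whether further studies are worthwhile.

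**The concern.** Random allocation makes the two schedules comparable at the start. Completion is decided later and can depend on the schedule, on how treatment is going, or on both. Once the comparison is limited to completers, any difference in who completes is mixed with the effect of the schedule.

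The exposure differs by outcome. Movement per aligner does not require a finished course, so the issue there is ordinary, possibly informative drop-out. Length of treatment does require one: a non-completer has no finished length and leaves that comparison by definition.

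At stake is the decision the study was sized to inform. A reader deciding whether to launch a further trial cannot tell whether the 17 came mainly from one schedule, why they stopped, or whether they were moving well or badly when they did.

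**Working it through.** **Disposition as printed.** 73 + 17 = 90 and 70 female + 20 male = 90, so the counts agree. Non-completion is 17/90 = 18.9%.

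**What cannot be reproduced.** The document gives no alpha, power, effect size, SD, drop-out allowance or arm sizes, so no corrected effect can be computed. What follows is illustration, with 45 per arm **assumed**.

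**How far the difference between arms can move.** Let f be the share of an arm that did not complete, and d the completer mean minus the non-completer mean in that arm, in SD units. The all-subject mean of the arm is its completer mean minus f × d. Hence

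completer difference − all-subject difference = f1 × d1 − f0 × d0.

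If d is 0 in both arms, nothing moves. If d is 1 SD in size (assumed) where a shift is stated:

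| Split of the 17 | Shift of 1 SD | Calculation | Movement |
|---|---|---|---|
| Even (8.5 each) | Same in both arms | 8.5/45 − 8.5/45 | 0 |
| 8 / 9 | Same in both arms | 9/45 − 8/45 | 0.02 SD |
| 12 / 5 | Same in both arms | 12/45 − 5/45 | 0.16 SD |
| Even | One arm only | 8.5/45 | 0.19 SD |
| 12 / 5 | 12-loss arm only | 12/45 | 0.27 SD |
| Any | Opposite in the two arms | 17/45 | 0.38 SD |

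Each movement can go in either direction. The 12/5 split is not far-fetched: if schedule had no bearing on stopping, a split at least that uneven would still occur with probability 10.4% (hypergeometric, 17 losses among 45 + 45).

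**Yardstick.** With 45 − 12 = 33 and 45 − 5 = 40 completers, the 95% half-width for the difference is 1.993 × √(1/33 + 1/40) = 0.47 SD. So the movement ranges from nothing to most of the half-width.

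**Precision.** Comparing √(1/45 + 1/45) = 0.211 with the completer standard error:

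- even split: √(2/36.5) = 0.234, narrowing 9.9%
- 12/5: √(1/33 + 1/40) = 0.235, narrowing 10.4%
- 17/0: √(1/28 + 1/45) = 0.241, narrowing 12.4%

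Using all 90 would narrow the interval by about 10 to 12%, and only if outcomes exist for the 17.

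**Length in weeks.** Assume equal aligner counts and full adherence, so that the 14-day course takes twice as long. With the stated 78-week average and equal arms this is 52 v 104 weeks. Assume a coefficient of variation of 0.4, giving SDs of 0.4 × 52 = 20.8 and 0.4 × 104 = 41.6 weeks. With shifts of 1 SD, the largest movement over all splits has all 17 in the 14-day arm: 17/45 × 41.6 = 15.7 weeks. A true 52-week difference would appear as 36.3 to 67.7 weeks: distorted by up to 30%, not reversed.

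**The case against.** The strongest reply has five parts.

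- *The text does not say that the 17 were excluded.* True. Exclusion is the natural reading, not a stated fact. If the 17 were analysed, one sentence would settle it, and the document still needs that sentence.
- *Nothing was hidden.* Also true. A reader might infer concealed selection, but the Results row prints the counts and names the completers as analysed. What is missing is the breakdown of the 17.
- *Baseline comparability was checked.* The discriminant analysis compares study groups on baseline features. If run on the 73, it speaks to measured imbalance among completers. It cannot detect selection related to outcome, it does not compare completers with non-completers, and the set it used is not given.
- *The study is exploratory, with no stated alpha.* This is why no error rate is claimed here. It does not remove the need to know which subjects produced the result.
- *A 7-day and a 14-day schedule will differ in weeks anyway.* Largely conceded, as the weeks calculation shows. It does not help for millimetres per aligner, where no difference is a credible result. Nor would it help if length were counted in aligners, as the Secondary Outcome row has it ("Length of treatment change was calculated as number of clear aligners used"). The two definitions of length are a separate point.

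**Conclusion.** The point stands and should be fixed. The only named analysis set is selected after allocation, the 17 are not described, and no analysis by assigned schedule or sensitivity analysis is given.

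The document supports exposure to bias, not a finding of bias. A reader might infer that the reported comparison is biased, or biased towards one schedule. Neither follows: if the 17 resemble the completers in each arm, or differ from them equally in both arms with an even split, the completer difference is unaffected. The 0 to 0.38 SD range rests on the assumed 45 per arm and the assumed 1 SD gap; a larger gap would move the difference further.

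Two limits apply. Taking the 90 starters as the randomised number is an inference from the 90 recruited. And randomisation is described only for wear schedule. The Statistical Analysis Plan row also refers to the "analysis of the efficacy of the aligners and the aligners with movement enhancement techniques", but the document does not say that enhancement was randomly assigned, so the loss of a randomised comparison is clear only for 7 v 14 days. Which groups are compared is a separate question.

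**What to change.** Label all of the following post hoc.

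1. Report the 17 by assigned schedule, reason and time of stopping. Compare their baseline features with those of the completers, and state which set the discriminant analysis used. Say what starting and completing mean.
2. For movement per aligner, analyse all randomised subjects by assigned schedule, using whatever on-treatment records exist. Add a sensitivity analysis that shifts the unobserved values in each arm, in both directions, and report the shift at which the conclusion changes.
3. For length of treatment, apply the same shift analysis and report the proportion completing by schedule among all 90.
4. Keep the 73-subject result, label it as completers only, and do not present it alone as the randomised comparison.

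The cost is one table, some text and a modest re-analysis of existing records. The downsides are the post hoc status, a result that may be less favourable or less certain, and possibly little movement data for the 17, since the document describes no measurement schedule. Where no such records exist, the shift analysis carries the weight.
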